Difference test is used for safety evaluation indicators. Two independent samples t test is used for measurement data. Pearson X2 test or Fisher's exact test is used for enumeration data. The adverse events and device defects occurred in this trial are described in list.

Difference test is used to evaluate the operating performance of the stapler. Pearson *X*2 test or Fisher exact test is used to analyze enumeration data. Center effect is considered during the analysis process. General linear model is used for measurement data. CMH is used for enumeration data.

Statistical Analysis

Trial Flow Chart

Visit Time	Visit 1	Visit 2	Visit 3	Visit 4
	Before surgery	During surgery	After surgery	After surgery
Visit Item	(Day $-7 \sim 0$)	(Day 0)	(Day 7 ± 2 days)	(Day 30 ± 5 days)
Informed consent	A			
Subject screening	A			
Demographic data	A			
History of present illness	A			
Past medical history	A			
Vital signs	A	A	A	A
Blood routine	A		A	
Coagulation routine	A		A	
Blood biochemistry	A		A	
Cardiac examination	A		A	A
Pulmonary function test	A			
Arterial blood gas	A			
analysis	_			
Preoperative imaging	A			
Blood pregnancy test	A			
Randomization		A		
Intraoperative		A		
observation record		_		
Use of device		A		
Postoperative imaging			A	
Postoperative follow-up			A	A
observation			_	_
Concomitant medication	A	A	A	A
Adverse events	A	A	A	A
Device defect		A		

List of Abbreviations

Abbreviation	English	Chinese
AE	Adverse Events	不良事件
CRF	Case Report Form	病例报告表
EC	Ethics Committee	伦理委员会
FAS	Full Analysis Set	全分析集
GCP	Good Clinical Practice	医疗器械临床试验质量管理规范
ICF	Informed Consent Form	知情同意书
PPS	Per-Protocol Set	符合方案集
SAE	Serious Adverse Events	严重不良事件
SOP	Standard Operating Procedure	标准操作规程
SS	Safety Set	安全数据集

Text of Study Protocol

1. Sponsor Information

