8.1.2 Secondary objectives

To evaluate whether there are differences in the secondary evaluation indicators when the Disposable Powered Articulating Endoscopic Linear Cutter Stapler manufactured by Fengh Company is used in gastrointestinal tissue cutting and anastomosis compared with the similar product manufactured by Johnson & Johnson Company.

To evaluate whether there are differences in the safety evaluation indicators (e.g., incidence of AEs, incidence of SAEs, incidence of device defects) between the Disposable Powered Articulating Endoscopic Linear Cutter Stapler manufactured by Fengh Company and the similar product manufactured by Johnson & Johnson Company in gastrointestinal tissue cutting and anastomosis.

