Formula: Incidence rate of anastomotic stricture infection = eligible subjects in each group/total number of subjects in the group \times 100%

(6) Incidence of SAE (serious adverse event)

Evaluation time: During the whole clinical trial process.

Evaluation method: Serious adverse event refers to an event occurs in the process of clinical trials, which results in death or serious deterioration of health, including fatal disease or injury, permanent damage to the body structure or function, requiring hospitalization or prolonging the hospitalization, requiring medical or surgical intervention to avoid the permanent damage to the body structure or function; results in fetal distress, fetal death or congenital abnormality, congenital defect, etc.

Formula: SAE incidence = number of subjects with SAE in this group/number of all subjects in this group \times 100%.

Precautions: The adverse events related to the anastomotic stoma during clinical trial shall be considered as serious adverse events. Since "anastomotic stoma repair" may be associated with "anastomotic stoma dehiscence", the "anastomotic stoma repair "is not repeatedly considered a serious adverse event.

(7) Incidence of AE (adverse event)

Evaluation time: During the whole clinical trial process.

Formula: Incidence of adverse events = number of subjects with adverse events in this group/number of all subjects in this group \times 100%.

Definition: An adverse event is any untoward medical occurrence in a clinical investigation, whether or not related to the device. It is necessary to analyze the postoperative vital signs and laboratory tests (blood routine, biochemical indicators, etc.).

(8) Incidence of device defects

Measurement time: During the whole process of clinical trial.

Calculation formula: Incidence of device defect = number of device defects/total number of devices × 100%.

Precautions: A test device defect that occurs during the course of a clinical trial. "Staple pop" due to human factors (e.g., incorrect reload selection) is not a defect of the device.

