8.2.6 Device using specification

According to the results of random allocation, the investigators apply the study medical device to the subjects who enter the test group, and the control medical device to the subjects who enter the control group. If a subject requires the use of a circular stapler during the trial, the brand and model of the circular stapler shall be recorded.

⁹ Only the conditions related to the use of test product and control product are recorded here. However, during the trial, subjects may use circular stapler or other staplers. If adverse events related to the stapler also occur, the occurrence shall be truthfully recorded in the adverse events.

¹⁰ It is necessary to use gas injection method for inspection. If relevant examination is not required, the CRF should be completed as "Not Applicable".

¹¹ If yes, please specify the reason and whether it is related to the stapler.

¹² The model and amount used in the clinical trial shall be truthfully recorded. Meanwhile, whether the subject uses the brand and model of circular stapler shall also be collected.

¹³ Investigators faithfully record whether each reload is used laparoscopically or laparotomically.

¹⁴ The tissues cut and anastomosed by each cartridge, such as stomach, duodenum, jejunum, ileum, appendix, ascending colon, transverse colon, descending colon, sigmoid colon and rectum, etc. are recorded.

¹⁵ If corresponding symptoms occur, the reasons for confirming the event should also be briefly described, so as to facilitate the review. In addition, generally anastomotic bleeding is judged by the presence or absence of persistent fresh bleeding from the gastric tube, and the diagnosis is confirmed by gastroscopy or second surgical exploration.

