9.7.1 Statistical method for data

Statistical analysis is performed using the SAS 9.1 software.

Statistical description on all data, including demographic data, baseline data, all efficacy indicators and all safety data shall be performed. Measurement data will be statistically described using mean, standard deviation, minimum, maximum, median, 25th percentile and 75th percentile; enumeration data will be statistically described using frequency and percentage.

The primary effectiveness evaluation indicator (anastomosis success rate) is evaluated by the confidence interval method.

The secondary evaluation indicators are evaluated by the difference test. Measurement data are compared using two independent samples t-test or Wilcoxon rank sum test. Enumeration data are compared using Pearson's X^2 test or Fisher's exact test.

The safety evaluation indicators are evaluated by the difference test. Enumeration data are compared using Pearson's X^2 test or Fisher's exact test. The adverse events and device defects occur in this trial shall be shown in list.

The stapler operational performance is evaluated by the difference test. Enumeration data are compared using Pearson's X^2 test or Fisher's exact test.

The central effect is considered in the analysis process. The general linear model is used for measurement data, and CMH or logistic regression is used for enumeration data.

9.7.2 Missing, unused, or incorrect data (including dropouts and withdrawals) and unreasonable data

All missing, unused or incorrect data (including dropouts and withdrawals) and unreasonable data will be discussed and finally determined by the investigators and biostatistician in the data review stage. The basic statistical principles for the processing of these data are as follows:

- (1) The details of each drop-out case shall be described, and the drop-out between the test group and the control group shall be compared using Pearson X^2 test or Fisher exact test;
- (2) Missing data at baseline shall not be estimated;
- (3) Missing values of main evaluation indicator (success rate of anastomosis) shall not be estimated;

Clinical Trial on Performance and Safety of Disposable Powered Articulating Endoscopic Linear Cutter Stapler in Gastrointestinal Tissue Cutting and Anastomosis

- (4) Missing values of secondary evaluation indicators shall not be estimated;
- (5) Missing values for operational performance evaluation shall not estimated;

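### Device defect incidence is defects per device rather than a proportion of subjects, so the implied chi-square or Fisher comparison is not well defined and, if reloads count as devices, can understate the p-value.

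*Combined protocol and SAP*

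**What the plan says.** Section 8.1.16 lists eight safety indicators. Items 1 to 7 are subjects with the event over subjects in the group. Item 8, device defects, is instead "number of device defects/total number of devices". The word device is not defined there as stapler, reload or both.

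Section 8.1.2 sets the secondary objective of looking for between-group differences in safety indicators and gives as examples "incidence of AEs, incidence of SAEs, incidence of device defects". Section 9.5 sets the level for safety indicators at 0.05. Section 9.7.1 states "The safety evaluation indicators are evaluated by the difference test" and offers Pearson's chi-square or Fisher's exact test for count data. The only adjustment named there is for centre, by CMH or logistic regression.

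The same section adds "The adverse events and device defects occur in this trial shall be shown in list", and the statistical part of the abstract has a matching sentence: "The adverse events and device defects occurred in this trial are described in list". The abstract's own list of safety indicators has seven items and leaves device defects out.

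On use of devices, the footnotes printed under section 8.2.6 ask for the model and amount used, for the approach (laparoscopic or open) reload by reload, and for "The tissues cut and anastomosed by each cartridge". Section 7.1 describes the control stapler as intended for one patient. Section 8.1.17 asks whether one stapler can be fired repeatedly.

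**The concern.** Pearson's and Fisher's tests compare proportions made of independent units, each of which either has the event or does not. Item 8 departs from this in two ways.

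- **Numerator.** It counts defects, not defective devices. A device with two defects adds two to the numerator and one to the denominator. The column of devices without a defect, which a 2x2 table needs, then cannot be obtained by subtraction. This holds whatever the number of devices per subject.
- **Denominator.** If reloads count, one subject supplies a stapler and at least one reload. Defects in the same operation share a patient, a surgeon and a handle, and may share a batch, so they may well be correlated. Adjusting for centre does not deal with correlation within subject.

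The denominator also depends on how many reloads are fired after randomisation. A group that uses more reloads shows a lower rate for the same number of defects.

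At stake is the reading of a named safety comparison in a device registration trial. The primary endpoint is not involved.

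**Working it through.** **Figures in the plan.** The plan gives no defect rate, number of devices per subject, correlation or power for this indicator, so there is no stated figure to reproduce for it. The group size used below is the plan's own and does reproduce. Section 9.2.1 gives 97% success in both groups, margin 10%, one-sided alpha 0.025 and power 80%:

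- n = 2 x 0.97 x 0.03 x (1.960 + 0.842)^2 / 0.10^2 = 45.68
- corrected: (45.68/4) x [1 + sqrt(1 + 4/(45.68 x 0.10))]^2 = 64.1, rounded up to 65
- with 20% dropout: 65/0.80 = 81.25, rounded up to 82 per group, 164 in total

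**Assumed inputs.** Devices per subject m = 1, 3 or 5; intra-subject correlation (ICC) 0 to 0.30; defect rate 1%, 2% or 5%; at most one defect per device. The 0.05 level in section 9.5 is taken as two-sided, since its sidedness is not stated.

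**Approximation.** Design effect DE = 1 + (m - 1) x ICC. True alpha of a nominal 5% device-level test = 2 x [1 - Phi(1.96/sqrt(DE))].

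| m | ICC 0.05 | ICC 0.10 | ICC 0.30 |
|---|---|---|---|
| 1 | 0.050 | 0.050 | 0.050 |
| 3 | 0.062 (DE 1.1) | 0.074 (DE 1.2) | 0.121 (DE 1.6) |
| 5 | 0.074 (DE 1.2) | 0.098 (DE 1.4) | 0.186 (DE 2.2) |

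This is a large-sample formula of chi-square type. It does not describe Fisher's test when defects are rare, so both tests were also simulated.

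**Simulation.** Beta-binomial counts, 82 subjects per group, m devices each, no true difference, 20,000 runs, rejection at p < 0.05. Each cell gives Pearson / Fisher.

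| Rate | m | ICC 0 | ICC 0.05 | ICC 0.10 | ICC 0.30 |
|---|---|---|---|---|---|
| 1% | 3 | 0.046 / 0.008 | 0.053 / 0.011 | 0.061 / 0.015 | 0.102 / 0.035 |
| 1% | 5 | 0.043 / 0.018 | 0.059 / 0.030 | 0.086 / 0.044 | 0.171 / 0.101 |
| 2% | 3 | 0.047 / 0.021 | 0.059 / 0.027 | 0.068 / 0.034 | 0.117 / 0.067 |
| 2% | 5 | 0.048 / 0.030 | 0.070 / 0.046 | 0.089 / 0.061 | 0.179 / 0.139 |
| 5% | 3 | 0.050 / 0.032 | 0.061 / 0.041 | 0.069 / 0.046 | 0.119 / 0.088 |
| 5% | 5 | 0.047 / 0.034 | 0.072 / 0.055 | 0.101 / 0.079 | 0.184 / 0.156 |

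With m = 1, the 1%, 2% and 5% rates give 0.008, 0.032 and 0.041 for Pearson, and at most 0.016 for Fisher.

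Over the positive correlations, Pearson runs from 0.053 to 0.184 and Fisher from 0.011 to 0.156. With m = 1 or ICC = 0 neither test exceeds 0.05.

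**Dilution.** For a fixed number of defects, moving from 3 to 5 devices per subject multiplies the per-device rate by 3/5 = 0.60.

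**The case against.** The strongest reply is that device defects are not tested at all. The only analysis sentences that name them call for a listing, and the abstract leaves them out of its safety indicators. A reader might infer from the general safety rule that a Pearson or Fisher test is expressly prescribed for defects. It is not; no sentence says so. However, the listing sentence covers adverse events too, and their incidence is plainly compared between groups. With sections 8.1.2 and 9.5 alongside, the listing reads best as additional to the test. That remains an inference, and the text should settle it.

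Three further readings go beyond the documents:

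- **That several devices per subject are stated.** They are not. If the unit is the stapler, one per subject is plausible and the clustering argument falls away. It applies only if reloads count. Recording reloads one by one makes this possible but gives no number.
- **That the p-value is too small.** It can be, given more than one device per subject and positive correlation. Fisher's conservatism often offsets the effect when defects are rare: at a 1% rate it stays below 5% in five of the six positive-correlation settings tabulated.
- **That a confidence interval is too narrow.** The plan specifies an interval only for the primary indicator.

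Section 9.1 also leaves detail to a statistical analysis plan to be finalised before database lock, so a clustering method could still be added there. That stands, but it does not repair the formula in 8.1.16(8), whose numerator is wrong for a 2x2 test under any unit.

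**Conclusion.** The concern holds in conditional form, and its weight is minor.

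Without any assumption about devices per subject, the ratio in 8.1.16(8) need not be a proportion, its unit is undefined, and the test implied by 9.5 and 9.7.1 is not well defined for it.

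Conditionally, if reloads count as devices and defects correlate within subject, a device-level test can be anti-conservative: about 5% to 18% for Pearson and 1% to 16% for Fisher at a nominal 5%. The devices per subject, the correlation and the defect rate behind those ranges are all assumed, because the documents give none of them.

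Since section 9.5 reads p > 0.05 as no significant difference, p-values that are too small would tend to produce a spurious difference rather than hide a real one. Dilution by extra reloads could work the other way. The primary non-inferiority test and the sample size are untouched.

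**What to change.** In 8.1.16(8) and 9.7.1, make the between-group comparison the proportion of subjects with at least one device defect, by Fisher's test or by CMH stratified by centre. This uses the same unit as items 1 to 7. State that the listing is additional to this comparison.

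Define device, and report the per-device rate descriptively only, separately for staplers and reloads, with defective devices as the numerator. Any interval given for it should allow for clustering by subject.

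The cost is a change of wording before the analysis plan is finalised; the amount used and the use of each reload are already recorded. The small downside is fewer analysis units: 82 subjects per group in place of 246 to 410 devices (82 x 3 to 82 x 5). With few events, Fisher's test on 82 per group will be conservative.

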8.1.17 Operational performance evaluation

(1) Stapler operating performance evaluation

Measurement time: During the stapler operation process.

Evaluation method: ① Whether the single-handed operation of stapler is smooth; ② whether the stapler can fire normally; ③ whether the back-off is smooth after the completion of anastomosis, whether there is tissue entrapment, whether there is resistance; ④ whether the stapler can fire continuously for many times is reliable; ⑤ whether the stapler can completely cut off the tissue; ⑥ whether the battery supply is stable; ⑦ whether the electric cutting is smooth.

8.2 Test Process

8.2.1 Test Flow Chart

Visit Time	Visit 1	Visit 2	Visit 3	Visit 4
	Before surgery	During surgery	After surgery	After surgery
Visit Item	(Day $-7 \sim 0$)	(Day 0)	(Day 7 ± 2 days)	(Day 30 ± 5 days)
Informed consent	A			
Subject screening	A			
Demographic data	A			
History of present illness	A			
Past medical history	A			
Vital signs	A	A	A	A
Blood routine	A		A	
Coagulation routine	A		A	
Blood biochemistry	A		A	
Cardiac examination	A		A	A
Pulmonary function test	A			
Arterial blood gas analysis	A			
Preoperative imaging	A			
Blood pregnancy test ¹	A			
Randomization		A		
Intraoperative		A		
observation record		_		
Use of device		A		
Postoperative imaging ²			A	
Postoperative follow-up			A	A
observation				
Concomitant medication	A	A	A	A
Adverse events	A	A	A	A
Device defect		A		

¹ Only for women of childbearing potential.

² In case of anastomotic leakage and bleeding, the investigators may perform relevant examinations for the subjects according to actual needs.

8.2.2 Enrollment

The investigators screened the subjects according to the inclusion and exclusion criteria after obtaining their informed consent; before the day of conducting gastrointestinal tissue cutting and anastomosis, the subjects were randomly divided into the test group and the control group according to the random assignment instructions.

8.2.3 Randomization

The trial was stratified by clinical trial institutes with the randomization method of stratified blocks. The seed number and block length were determined with SAS9.1 statistical software programming. The subjects were divided into the test group and the control group in a ratio of 1:1. The random grouping arrangement of at least 164 subjects was generated, and the corresponding sequentially numbered, opaque and sealed randomization envelopes were made. The randomization envelopes were kept and allocated by relevant personnel who were not involved in the screening and treatment of subjects and authorized by the investigator.

The random number is a 4-digit sequential number consisting of "center number" and "serial number" (which is generally the "center digit occupied + sample size digit occupied"). The first digit is the number of the clinical trial institution, and the last 3 digits are the "serial number" assigned by randomization. When the serial number is less than 3 digits, add "0" to make up 3 digits. If the randomization number "1001" is the first randomization number of the clinical trial institute with the institute number of 01, it corresponds to the first subject randomized at the institute.

When a subject was determined to be enrolled, the investigators or other authorized designee requested randomization assignment from the randomization envelope manager. The randomization envelope keeper took out the randomization envelope in the order of random number, filled in the screening number and initials of the subject to be assigned to the designated place on the back of the envelope, and signed the name and date to complete the allocation. The investigators or other authorized designee then intervened based on the results of the randomization assignment (i.e., test groups).

8.2.4 Blinding method

The investigators could not be blinded due to the difference in appearance between the test device and the control device, this trial therefore adopted an incomplete blinding method, and the subjects were not informed of the randomization results (i.e., the subjects did not know their own treatment assignment).

8.2.5 Inspection items

8.2.5.1 Medical history and vital signs

- (1) Demographic data: gender, date of birth;
- (2) History of present illness: admission time, surgical site ³;
- (3) Past medical history: allergy history, dysfunction history of vital organs (heart, lung, liver and kidney), surgery history, and previous medication history ⁴ (within 1 month);
- (4) Vital signs: height, weight, blood pressure, pulse, temperature, respiration, BMI ⁵;

8.2.5.2 Laboratory examinations

- (1) Blood routine: hemoglobin (Hgb), red blood cell count (RBC), white blood cell count (WBC), neutrophil count (NEUT), neutrophil ratio (NEUT%), platelet count (PLT);
- (2) Coagulation blood routine: prothrombin time (PT), activated partial thromboplastin time (APTT), international normalized ratio (INR);
- (3) Cardiac examination: ECG, cardiac ejection fraction;
- (4) Fasting blood glucose ⁶;
- (5) Fecal examination: occult blood test;
- (6) Cardiac ultrasonography: cardiac ejection fraction;
- (7) Pulmonary function test: forced expiratory volume in one second (FEV1)/predicted value, forced expiratory volume in one second (FEV1)/forced vital capacity (FVC);
- (8) Blood pregnancy test: applicable to women of childbearing age (18 ~ 50 years old);

8.2.5.3 Preoperative imaging ⁷

(1) CT examination: tumor stage, whether there is liver metastasis, whether there is pelvic metastasis, whether there is lung metastasis;

8.2.5.4 Post-operative imaging 8

- (1) Angiography: whether there is anastomotic bleeding;
- (2) Upper gastrointestinal radiography: whether there is an astomotic leakage and stricture;

³ The data can be completed after the end of surgery.

⁴ Mainly record drugs that affect healing (e.g., antineoplastic agents, corticosteroids) or coagulation.

⁵ Body mass index (BMI) = weight (kg) ÷ height2 (m2)

⁶ Combined with clinical practice, the subjects enrolled in this trial are all hospitalized patients who will receive routine blood biochemical examination (including blood glucose item), and the blood glucose value in the blood biochemical results of hospitalized patients after blood collection in the morning is generally fasting blood glucose value; if the subject does not have fasting blood glucose value, the blood glucose value ($\leq 10.0 \text{ mmol/L}$) is also used for screening confirmation; this is acceptable to be the fasting blood glucose data in the screening period. The investigators may choose to do this according to the subject's condition.

⁷ If the subject is a non-tumor patient, such examination may not be performed, and the CRF should be completed as "Not Applicable".

⁸ In case of anastomotic leakage, stricture and bleeding, the investigators may decide whether the subject will receive angiography, upper gastrointestinal radiography and gastrointestinal endoscopy according to actual needs. If relevant examination is not required, the CRF should be completed as "Not Applicable".

Clinical Trial on Performance and Safety of Disposable Powered Articulating Endoscopic Linear Cutter Stapler in Gastrointestinal Tissue Cutting and Anastomosis

- (3) Gastrointestinal endoscopic examination: whether there is anastomotic leakage and stricture;
- (4) Abdominal CT: whether there is abdominal effusion and the amount of abdominal effusion;

8.2.5.5 Other tests:

- (1) Intraoperative observation items: name of operation, start time of operation, end time of operation, start time of anastomosis, end time of anastomosis and intraoperative blood loss;
- (2) Observation of the study product⁹: whether the digestive tract is successfully transected and stapled, whether the cutting anastomosis ring/staple line is complete, whether there is leakage of cutting anastomosis ring/staple line, whether there is bleeding of cutting anastomosis ring/staple line, whether there is bubble overflow at the anastomotic stoma¹⁰, whether there are indicators of conversion to laparotomy¹¹, number of needles for anastomotic repair¹¹, whether there is anastomotic dehiscence¹¹, whether there are other complications¹¹, whether the staple line or tissue buttressing materials are used, and the operating performance of stapler;
- (3) Device use¹²: model and specification of electric stapler, model of cartridge, use condition¹³, cutting and stapling tissues¹⁴, device defects;
- (4) Postoperative follow-up observation: first anus exhaust time, semi-liquid feeding time, first defecation time, bowel sound recovery time, whether there is anastomotic bleeding¹⁵, whether there is anastomotic leakage¹⁵, whether there is anastomotic stenosis¹⁵, whether there are other complications¹⁵, whether there is abdominal effusion and the abdominal effusion volume;
- (5) Routine observation items: adverse events, concomitant medication, protocol deviations.

